Study Title: Outcomes of sclerotherapy of the ulcer bed compared to a combination of ablation and injections

Principal Investigator: [name]

Sub Investigator: [name], PhD

Background:

Venous ulcers are the most common cause of ulcerations that affect the lower extremities and are estimated to effect 1% of the American population¹. They are responsible for more than 80% of lower extremity ulcerations²⁻⁴. Venous ulcers are most common in the elderly and in patients with a history of diabetes, obesity, varicose veins, blood clots, and edema of the lower extremities. Treatment is extensive averaging 6 to 12 months of continual therapy. Healing rates for these ulcers are poor and more than 50% of these types of ulcers are still unhealed after 9 months^{5,6}. Over 70% of those patients will end up developing another venous ulcer within 5 years¹. With these astounding numbers, it is imperative for early diagnosis and prompt treatment. Any underlying causes should also be assessed and determined at the time of diagnosis to help with healing and prevention.

Management of these ulcers has historically been compression treatment, stripping of the superficial veins, elevation of the effected leg, and exercise. Ablative superficial surgery along with compression is another form of treatment. Endovenous ablation is where the problematic vein is sealed off (generally the great saphenous vein (GSV) in the thigh or the short saphenous vein (SSV) behind the knee and calf). A catheter is fed up the vein from the ankle or knee level. It is carefully fed, using the aid of ultrasound, to the junction between the GSV and SSV. An electrical current or laser energy is passed through the vein wall causing the vein to contract and seal itself off. This procedure is quicker and less painful compared to the traditional operation of vein stripping. Early endovenous ablation of superficial venous reflux in addition to compression has resulted in shorter ulcer healing time and a reduction in the 12-month reoccurrence rate versus compression therapy alone^{7,8}.

Another popular form of treatment is sclerotherapy. Either a foam mixture or a solution is injected into the effected veins causing inflammation and scarring. Over time this leads to destruction of the veins. This treatment is also commonly used with compression therapy. This technique promotes rapid healing usually occurring within 4 to 8 weeks after the initial treatment and long term recurrence rates⁹. This route is much less invasive, quicker, and less painful than the historical procedure of vein stripping.

Although there have been several studies performed on the significance of endovenous ablation and sclerotherapy, there is very little data or evidence to support the effectiveness of endovenous ablation in addition to sclerotherapy and compression in the treatment of venous ulcers and their reoccurrence. There is also very little data on whether receiving sclerotherapy and ablation together at the start of treatment, has any benefit over receiving sclerotherapy at the start of treatment and conducting ablation at a later time.

Research Question

Do outcomes of sclerotherapy of the ulcer bed alone, differ from a combination of ablation and injections?

Specific Aims

Our specific aims for this study are as follows:

Efficacy:

1. To determine if receiving sclerotherapy and ablation along with compression therapy at the start of treatment (arm 1) has any benefit over receiving sclerotherapy at the start of treatment and ablation 3 months later along with compression therapy (arm 2) in the treatment of chronic venous ulcers.
2. To compare and determine which arm has improved scores for quality of life (using the VEINES-QOL/Sym questionnaire).
3. To compare and determine which arm has improved venous clinical severity scores (VCSS).
4. To determine ulcer outcome and need for retreatment in arm 1 versus arm 2.

Safety:

1. To determine which arm puts patients at greater risk of increased healing times in the treatment of chronic venous ulcers.

Methods

Patients who are treated at Jobst Vascular Institute (JVI) will be evaluated for potential enrollment in this prospective study. Those who qualify, or their legally authorized representative (LAR), will be approached with study information and informed consent. Patients, or their LAR, who agree to participate will be consented and enrolled in the study.

This will be a randomized clinical trial. Subjects will be randomly allocated to each group. There will be roughly equal number of subjects in each arm. Arm 1 will be patients receiving sclerotherapy and ablation at the start of treatment along with compression therapy. The patients in arm 1 will not receive any further treatment during the duration of the study. Arm 2 will be patients who receive sclerotherapy at the start of treatment along with compression therapy, and ablation 3 months later. All patients in arm 2 will receive ablation at their 3 month appointment. After ablation, the patients in arm 2 will not receive any further treatment for the remainder of the study.

30 opaque envelopes, 15 indicating arm 1 and 15 indicating arm 2, will be prepared by the study coordinator. Patients who agree to participate will select an envelope and treatment will be initiated based off of the arm that is selected. In the event of a participants early termination from the study, up to 5 study participants will be replaced in each study arm to help ensure an adequate number of subjects for analysis. The purpose of this study is to see if one treatment is more effective over the other in treating chronic venous ulcers.

Patients who participate will have ultrasound-guided sclerosant injected into the affected area. Half of the patients will only receive injections (arm 2) while the other half of the patients will receive injections along with ablation (arm 1). Patients in arm 1 will not receive any further

treatment during the remainder of the study. All patients will fill out a quality of life questionnaire (using the VEINES-QOL/Sym questionnaire) and complete the venous clinical severity score (VCSS) questionnaire prior to treatment. All patients will undergo compression therapy.

Patients will be seen weekly after treatment. Safety assessments will take place during these weekly appointments to ensure patient safety. After 3 months, patients will be brought in for another follow up visit. The 3 month follow up is considered standard protocol after these procedures to monitor for adverse events. Ulcer size, symptoms, healing rate, quality of life (using the VEINES-QOL/Sym questionnaire), and venous clinical severity score (VCSS) will be assessed. All patients in arm 2, will receive ablation at this time.

All patients will continue to be seen weekly to assess healing progress and to ensure patient safety. Six months following initial treatment, the patients will return for another follow up visit where ulcer size, symptoms, healing rate, quality of life (using the VEINES-QOL/Sym questionnaire), and VCSS will be assessed. Participation in the study will be complete after the 6 month follow up appointment. Patients will continue to see their physician for treatment, if needed, after their participation has concluded.

All treatments and appointments are considered standard of care and will be billed to the patients insurance.

Following completion of data collection (see study variables on attached excel sheet), analysis will be completed to identify study results. We will be analyzing the differences between the two groups in A. ulcer healing rate (comparison of means, generalized linear model), and B. proportion of healed ulcers (Chi square).

Inclusion/Exclusion Criteria

Inclusion Criteria:

- Patients 18 years of age and older
- Patients who have saphenous vein reflux and a single venous ulcer of any size

Exclusion Criteria:

- Patients under 18 years of age
- Patients with multiple venous ulcers

How Human Subjects will be involved

All enrolled subjects will have ultrasound-guided sclerosant injected into the affected area. At the start of treatment, half of the patients will receive injections at the start of treatment and ablation 3 months later (arm 2) while the other half of the patients will receive injections in addition to ablation at the start of treatment (arm 1). All patients will undergo compression therapy following treatment.

Risks/Side-effects

During the **sclerosant injections**, some people experience minor stinging or cramps when the needle is inserted into the vein. The risks associated with the injection include, but are not limited to, bruising, raised red areas, small skin sores, darkened skin in the form of lines or spots, and multiple tiny red blood vessels. These side effects usually go away within a few days to several weeks. Other more serious side effects include, but are not limited to, inflammation, blood clot, air bubbles and allergic reaction.

For **ablation**, if local anesthetic is used, the patient may experience slight pinpricks as the anesthetic is injected. They may also feel slight pressure when the catheter is inserted. The risks associated with an ablation include but are not limited to, infection, blood vessel damage, swelling, pain over the treated vein, nerve damage, and bruising or bleeding at the puncture site.

Benefits

Patients may or may not receive any personal benefits from being in this study. It is anticipated that other people may benefit from the results of this study in the future.

Number of Subjects

Up to 40 subjects. The goal is to enroll 15 subjects in each arm. In the event of a participants early termination from the study, up to 5 study participants will be replaced in each study arm to help ensure an adequate number of subjects for analysis.

Confidentiality

All data will be kept private. The study team has taken steps to protect participant privacy. The research investigators cannot guarantee absolute confidentiality. Only the authorized people described in this application will have access to participant information and results. The ProMedica Health System Institutional Review Board also may have access to study records. Data will be stored in a password protected computer at a secured location with access limited to research staff. Patients included with this study will be assigned a unique identifier to maintain confidentiality and the de-identified data set will be used for analysis. Any reports regarding outcome data will be presented in aggregate, without any patient identifiers.

Dissemination of Results

Pending results, it is anticipated that significant findings will be submitted to peer-reviewed journals for publication and may also be submitted as an abstract to appropriate scientific meetings.

References:

1. Terrie YC, (2017). Recognizing and Treating Venous Stasis Ulcers. *US Pharm.* 2017. 42(2):36-39.
2. Agale SV, (2013). Chronic leg ulcers: epidemiology, aetiopathogenesis, and management. *Ulcers*, 2013:413604.
3. de Araujo T, Valencia I, Federman DG, Kirsner RS, (2003). Managing the patient with venous ulcers. *Ann Intern Med*, 138(4):326-334.
5. Gabriel A. Vascular ulcers. *Medscape*. <http://emedicine.medscape.com/article/1298345-overview#a6>. Accessed November 1, 2016.

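### The only safety aim is a healing outcome and no adverse-event comparison is planned, so a safety conclusion could rest on healing alone

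*Combined protocol and SAP*

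**What the plan says.** All references are to the combined protocol and SAP.

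- **Specific Aims, Safety.** There is one aim: "To determine which arm puts patients at greater risk of increased healing times in the treatment of chronic venous ulcers".
- **Methods, analysis paragraph.** The between-arm analyses are "A. ulcer healing rate (comparison of means, generalized linear model), and B. proportion of healed ulcers (Chi square". Nothing else is listed.
- **Methods, visits.** For the weekly visits after treatment: "Safety assessments will take place during these weekly appointments to ensure patient safety". For the 3-month visit: "The 3 month follow up is considered standard protocol after these procedures to monitor for adverse events". For months 3 to 6: "All patients will continue to be seen weekly to assess healing progress and to ensure patient safety".
- **Risks/Side-effects.** For injections: "Other more serious side effects include, but are not limited to, inflammation, blood clot, air bubbles and allergic reaction". For ablation the list includes "infection, blood vessel damage, swelling, pain over the treated vein, nerve damage", as well as bruising or bleeding at the puncture site.
- **Number of Subjects.** The goal is 15 per arm, with up to 5 replacements per arm and a maximum of 40.

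The study variables are in an attached spreadsheet that is not part of the supplied text.

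**The concern.** Time to healing is the benefit these treatments seek. The Background itself presents shorter healing as a gain from early ablation. Here it is the whole content of the safety aim, while the harms that the protocol names appear only as risk information. Someone following the plan would address safety from healing results and would have no instruction to set harms side by side by arm.

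This matters because the randomised contrast is the timing of ablation relative to sclerotherapy: together at the start, or 3 months apart. Procedural harm could differ on exactly that contrast. An arm could heal faster and also have more clots, infections or nerve injuries, and the stated aim would still favour it on safety.

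**Working it through.** **1. Aims against analyses.** Safety aims: 1, of which 0 concern adverse events. Between-arm analyses: 2 (healing rate, proportion healed), of which 0 concern adverse events. Time to healing is not named in the analysis list either. The nearest item is healing rate, so even the stated safety aim has no explicitly matching analysis. The plan gives no safety figure to reproduce.

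**2. Follow-up available for a harms comparison.** Participation ends at month 6 in both arms.

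- From first treatment: 6 months in arm 1 and 6 months in arm 2.
- From ablation: 6 − 0 = 6 months in arm 1, and 6 − 3 = 3 months in arm 2.

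A comparison of the two strategies from first treatment therefore has equal planned follow-up. Only a comparison timed from ablation has unequal windows.

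**3. Patients per arm.** Target 15; with all replacements 15 + 5 = 20; both arms 2 × 20 = 40, which agrees with the stated maximum.

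**4. What zero events would mean.** The two-sided exact (Clopper-Pearson) 95% upper limit for 0 of n is 1 − 0.025^(1/n).

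- n = 15: 1 − 0.025^(1/15) = 0.218, or 21.8%.
- n = 20: 1 − 0.025^(1/20) = 0.168, or 16.8%.

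**5. Chance of seeing a harm at all in one arm.** The documents give no event rates, so the rates below are assumptions. The formula is 1 − (1 − p)^n.

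| Assumed true risk | n = 15 | n = 20 |
|---|---|---|
| 1% | 14% | 18% |
| 5% | 54% | 64% |
| 10% | 79% | 88% |

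**6. Whether a test would help.** This step assumes two-sided alpha 0.05 and Fisher's exact test. For k of 15 against 0 of 15, the two-sided p-value is 2 × C(15,k)/C(30,k).

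- k = 4: 2 × 1365/27405 = 0.100.
- k = 5: 2 × 3003/142506 = 0.042.

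So at least 5 against 0 is needed. Power is the sum of the binomial probabilities of all outcome pairs with p < 0.05. With 15 per arm and assumed risks it is 8% for 5% against 20%, 15% for 10% against 30%, and 74% for 5% against 50%. A harms comparison at this size can describe. It cannot establish that one arm is safer unless the difference is very large.

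**The case against.** The strongest reply is that the protocol does look after safety. It plans weekly assessments to month 6 and ties the 3-month visit to adverse events. It sets no rule for declaring an arm safer, and it states its purpose as effectiveness. Prolonged ulceration while ablation is delayed is arguably itself a harm, so part of the problem is labelling. The spreadsheet may contain adverse-event fields.

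Much of this stands, and it rules out three stronger readings that a reader might infer.

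- *That the trial would have no safety data.* The scheduled assessments contradict this. What is absent from the text is a defined adverse-event outcome and a summary by arm.
- *That the weekly safety data are certain to be available for analysis.* The text says that assessments take place. It does not say what is recorded, how events are graded or how they are attributed, and the spreadsheet cannot be checked.
- *That unequal time after ablation makes an adverse-event table by arm invalid.* It does not. Both randomised strategies are followed for 6 months from first treatment, and that is a fair comparison of strategies.

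Two practical cautions also stand. The risk section separates more serious effects for injections but not for ablation, so it does not supply a definition of seriousness. Bruising is listed for both procedures, so a count of patients with any event could be dominated by minor ones.

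None of this removes the defect. Even if the spreadsheet has adverse-event fields, the analysis paragraph plans no comparison of them, and the only aim labelled safety would still be answered with healing.

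**Conclusion.** The concern holds in this form: the sole safety aim is a healing outcome and neither planned analysis concerns adverse events, so a safety conclusion could rest on healing alone while the named procedural harms go uncompared. This is a fault in the stated aim and its analysis. It is not a claim that patients are unmonitored or that an unsupported safety conclusion is certain to be drawn.

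The limits of 21.8% for 0 of 15 and 16.8% for 0 of 20 follow from the sample size. They do not measure the defect and would be the same under a full adverse-event plan. They show how modest any safety statement must be. The detection and power figures rest on assumed event rates, and the power figures also on an assumed alpha. The healing analyses are not affected by this point.

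**What to change.** 1. Move healing time to the efficacy aims.
2. Restate the safety aim as a descriptive comparison between randomised arms of the number of patients with at least one adverse event from the protocol's own risk list, and with at least one serious event, from first treatment to month 6. Define serious in advance for both procedures, and also show counts by event type so that minor events do not hide rarer ones.
3. Count every randomised and treated patient, including those who leave early and are replaced, so the denominator may reach 20 per arm.
4. Report counts with exact (Clopper-Pearson) 95% intervals per arm and a risk difference with its interval. Make no claim that an arm is safer on the basis of healing or of zero events, and quote the upper limit that applies to the number treated.
5. As a secondary description, report events within 3 months after each procedure. Note that in arm 1 both procedures share one window, so events cannot be assigned to either. Note also that arm 2's post-ablation window includes only patients who reach month 3, a subset formed after randomisation.

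The cost is a reworded aim and one analysis paragraph, with no extra patients or visits. If the variable spreadsheet has no adverse-event fields, a few must be added to the weekly visit record. The downside is small: the intervals will be wide and the safety statement correspondingly modest.

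### The Research Question asks about sclerotherapy alone, but all of arm 2 is ablated at 3 months and the planned tests name no visit

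*Combined protocol and SAP*

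**What the plan says.** Two comparisons appear in the combined protocol and SAP.

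- **Sclerotherapy without ablation versus the combination.** The Research Question asks "Do outcomes of sclerotherapy of the ulcer bed alone, differ from a combination of ablation and injections". The Study Title sets the same contrast without the word alone: "Outcomes of sclerotherapy of the ulcer bed compared to a combination of ablation and injections".
- **Ablation now versus ablation later.** Specific Aims (Efficacy 1) asks whether immediate ablation "has any benefit over receiving sclerotherapy at the start of treatment and ablation 3 months later along with compression therapy (arm 2"). The arm definitions in Methods and the section on how human subjects will be involved describe the same contrast. Methods is categorical: "All patients in arm 2 will receive ablation at their 3 month appointment", with no exception for ulcers already healed.

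The Background lists both as separate evidence gaps: first that "there is very little data or evidence to support the effectiveness of endovenous ablation in addition to sclerotherapy and compression", then whether giving both together "has any benefit over receiving sclerotherapy at the start of treatment and conducting ablation at a later time".

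Ulcer size, symptoms, healing rate, VEINES-QOL/Sym and VCSS are assessed at 3 months and again at 6 months. The analysis paragraph at the end of Methods gives two between-arm tests: healing rate (comparison of means, generalized linear model) and proportion healed (chi-square). It names no visit for either. It points to an attached variables sheet, which was not among the documents available.

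Of the 3-month visit, Methods says "All patients in arm 2, will receive ablation at this time", without stating whether the assessments come first. Methods also says "Half of the patients will only receive injections (arm 2"). That probably describes initial treatment only; it needs clarifying but is not treated here as a second design.

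**The concern.** Arm 2 is on sclerotherapy alone only from baseline to the 3-month visit. After that, both arms have been assigned ablation. The two questions therefore have different estimands and different valid time windows, and the analysis text does not tie either test to a window.

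A 6-month test fits the plan as written and is a valid test of Aim 1. Reported under the present title and Research Question, however, it would be read as evidence on sclerotherapy alone, which it does not estimate. If the visit is chosen after the data are seen, the result can also choose the question.

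**Working it through.** **What each visit can estimate**

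| Period | Arm 1 | Arm 2 | Contrast |
|---|---|---|---|
| Baseline to 3-month visit, before arm 2 ablation | sclerotherapy + ablation | sclerotherapy | combination vs alone (Research Question) |
| Baseline to 6 months | sclerotherapy + ablation | sclerotherapy, ablation at month 3 | immediate vs deferred (Aim 1) |

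This is enough to establish the mismatch. The documents give no effect size, arm-specific healing rate or power figure, so there is no stated number to reproduce. The rest is an illustration of size.

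**Inputs, all assumed**

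- Base healing: 50% unhealed at 9 months (39 weeks) on sclerotherapy alone. The Background says more than half, for venous ulcers generally. Weekly hazard h = ln 2 / 39 = 0.0178.
- Ablation multiplies the hazard by a hazard ratio (HR) of 1.5 to 3, starting 0, 6 or 12 weeks after the procedure.
- Arm 2 ablation at week 13; visits at weeks 13 and 26.
- Proportion healed = 1 − exp(−cumulative hazard).

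**Base case, HR 2, no lag, 6 months**

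- Arm 1: 1 − exp(−2 × 26h) = 60.3%.
- Arm 2 as designed: 1 − exp(−(13h + 2 × 13h)) = 1 − exp(−39h) = 50.0%.
- Arm 2 had it stayed on sclerotherapy alone: 1 − exp(−26h) = 37.0%.
- Gap as designed: 10.3 points. Gap against alone: 23.3 points. Ratio 0.44.

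**Other cases at 50% unhealed** (gaps in points, taken before rounding)

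| HR | Lag (weeks) | Arm 1 / deferred / alone at 6 months (%) | Gap vs deferred | Gap vs alone | Ratio |
|---|---|---|---|---|---|
| 1.5 | 0 | 50.0 / 43.9 / 37.0 | 6.1 | 13.0 | 0.47 |
| 2 | 0 | 60.3 / 50.0 / 37.0 | 10.3 | 23.3 | 0.44 |
| 2 | 6 | 55.8 / 44.4 / 37.0 | 11.5 | 18.8 | 0.61 |
| 2 | 12 | 50.9 / 38.1 / 37.0 | 12.8 | 13.9 | 0.92 |
| 3 | 0 | 75.0 / 60.3 / 37.0 | 14.7 | 38.0 | 0.39 |

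Over the full grid (HR 1.5 to 3, lag 0 to 12 weeks) the ratio runs from 0.39 to 0.92.

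**Sensitivity**

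- 70% unhealed at 9 months (h = −ln 0.7 / 39), HR 2: 7.8 vs 16.7 points with no lag (0.47); 8.8 vs 9.5 with a 12-week lag (0.92).
- A different parameterisation, with 30% to 50% healed at 3 months on sclerotherapy, HR 1.5 to 3 and no lag: 5 to 12 points as designed against 13 to 37 vs alone, a ratio of 0.20 to 0.46.
- Fast healing: the Background says sclerotherapy usually heals ulcers in 4 to 8 weeks. Taking that as 75% healed by week 8 (h = −ln 0.25 / 8), HR 2, no lag, the 6-month gaps are 0.1 and 1.1 points, because nearly every ulcer has healed.

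**Healing rate.** Suppose ablation adds a fixed amount d to the weekly rate and no ulcer heals before 6 months. The mean-rate gap over 26 weeks is d(26 − lag)/26 against alone and 13d/26 against deferred. The ratio is 13/(26 − lag): 0.50, 0.65 and 0.93 for lags of 0, 6 and 12 weeks.

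**Power** (exact double binomial sum, uncorrected Pearson chi-square, two-sided 5%, 15 per arm, 50% unhealed). Over the grid it is 5% to 40% at 3 months and 6% to 22% at 6 months. At HR 2:

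| Lag (weeks) | 3 months | 6 months as designed |
|---|---|---|
| 0 | 17.6% | 8.2% |
| 6 | 9.5% | 8.9% |
| 12 | 5.2% | 10.1% |

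A true alone-versus-combination test at 6 months (HR 2, no lag) would have 23.6%.

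**The case against.** The strongest reply is that the operative text describes one design. Aim 1, the arm definitions, both month-3 ablation sentences and the human-subjects section all say immediate versus deferred. The outlier is one loosely worded Research Question, plus a title that never says alone. On that view a 6-month test is correct and only wording needs tidying. The description of the design is fair, and the 6-month test is valid for Aim 1. But the Research Question is the plan's own statement of what it asks, and the Background treats the two as different gaps, so the conflict stands.

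Second, in every modelled case the 6-month contrast has the same sign as alone-versus-combination and is merely smaller. That is true under these models, so a clear positive result would carry directional information. Its size, and any null result, would still not answer the question asked.

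Third, 3 months is not uniformly the better proxy for a 6-month effect against sclerotherapy alone. At HR 2 with a 6-week lag, that effect is 18.8 points; the 6-month contrast gives 11.5 and the 3-month contrast 9.3. With a 12-week lag the figures are 13.9, 12.8 and 1.4. This stands. The 3-month data answer the question as of 3 months and no later.

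Fourth, the magnitudes are assumptions throughout, and the variables sheet may tie variables to visits. Both are accepted. Neither removes the conflict between the Research Question and Aim 1. The order of events at the 3-month visit may well be assessments first, as the text lists them, but it should be stated. No passage plans to report a 6-month result as being about sclerotherapy alone; the plan simply does not prevent it.

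**Conclusion.** The concern holds. As supplied, the plan asks about sclerotherapy alone, ablates all of arm 2 at month 3, and allows its tests at a visit where the alone condition no longer exists. That conclusion follows from the text and does not depend on the illustration.

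With 50% unhealed at 9 months, HR 1.5 to 3 and a lag of 0 to 12 weeks, the 6-month contrast understates the 6-month difference against sclerotherapy alone by about 8% to 61%. The lag before ablation acts drives most of that range. If healing is as fast as the Background suggests for sclerotherapy, both gaps are about 1 point or less. The size is therefore not established; the mismatch is, subject to the unseen sheet on the question of visits. It should be corrected because the main conclusion could otherwise be attached to the wrong question.

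**What to change.** 1. The sponsor reconciles the Study Title, the Research Question, Aim 1 and the descriptions of arm 2 in Methods, and states which question is primary.
2. Add text such as: *Any conclusion about sclerotherapy alone uses only data from baseline to the 3-month visit, with ulcer, VEINES-QOL/Sym and VCSS assessments completed before the arm 2 ablation. The 6-month comparison is labelled immediate versus 3-month-deferred ablation.*
3. Name the visit for each planned test to match the chosen question, and report the difference between arms with a 95% confidence interval.

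No change to the treatment schedule is proposed, and no new data are needed, since both arms already have the same assessments at 3 and 6 months. The cost is wording, with three consequences to accept. The comparison not chosen becomes secondary. Sclerotherapy alone can be judged only up to 3 months, where the gap may be small if ablation acts slowly (HR 2, 50% unhealed: 16.4 points with no lag, 9.3 with a 6-week lag, 1.4 with a 12-week lag). Power with 15 per arm stays low at either visit.

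### Early leavers are replaced to keep up the number analysed, but no analysis set is named and nothing says how leavers' outcomes enter the two planned comparisons.

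*Combined protocol and SAP*

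**What the plan says.** Methods and Number of Subjects give the same rule: after an early termination, "up to 5 study participants will be replaced in each study arm to help ensure an adequate number of subjects for analysis". Number of Subjects sets the size: "Up to 40 subjects. The goal is to enroll 15 subjects in each arm". Early termination is not defined.

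The analysis paragraph at the end of Methods lists two comparisons between the groups: ulcer healing rate (means, generalized linear model) and proportion of ulcers healed (chi-square). It names no analysis set, no time point for the healed proportion and no method for missing outcomes.

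Follow-up of patients who remain is clear. After the 3-month visit, "All patients will continue to be seen weekly to assess healing progress and to ensure patient safety", and they return at 6 months for assessment of the ulcer.

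Methods also limits treatment. For arm 1, "The patients in arm 1 will not receive any further treatment during the duration of the study". For arm 2, "After ablation, the patients in arm 2 will not receive any further treatment for the remainder of the study". Treatment as needed is mentioned only for the period after the study: "Patients will continue to see their physician for treatment, if needed, after their participation has concluded".

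**The concern.** Replacing a leaver helps secure the number analysed only if the leaver is not part of that number. The rule therefore points to a comparison of those who stayed, which is no longer the comparison that randomisation set up.

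This matters if leaving depends on how the ulcer is doing. The treatment limits give one possible route: a patient whose ulcer is failing can have no further procedure within the protocol and may leave to get one. If such patients drop out of the analysis, their arm's healed proportion is inflated, and the difference shifts toward the arm that loses more failures. Because the plan is silent, the choice of whom to analyse could also be made after the results are known.

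**Working it through.** **The plan's own figure.** 2 arms × (15 + 5) = 40, which matches the stated ceiling. At the ceiling, leavers are 5/20 = 25% of each arm and 10/40 = 25% overall.

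**Inputs.** From the protocol: 15 per arm to be analysed, and up to 5 replaced per arm. Assumed, because the protocol gives no figure: true healing p = 50% (range 30% to 70%), the number of leavers k, and leavers who are unhealed and excluded.

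**One arm, with replacement.** To finish with 15, the arm randomises 15 + k. Expected healed is (15 + k)p, and all of these are among the 15 analysed, so the observed proportion is (15 + k)p/15.

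| Leavers k | p = 50% |
|---|---|
| 1 | 8/15 = 53.3% |
| 2 | 8.5/15 = 56.7% |
| 3 | 9/15 = 60.0% |
| 5 | 10/15 = 66.7% |

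For k = 3 over the range: at p = 30%, 5.4/15 = 36% (+6 points); at p = 70%, 12.6/15 = 84% (+14 points).

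**Is replacement the cause?** Without it, the observed proportion is 15p/(15 − k). At p = 50% and k = 3 this is 7.5/12 = 62.5%, slightly worse than 60%. Exclusion causes the inflation; replacement dilutes it a little.

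**Between arms, no true difference.** The spurious difference is (k₁ − k₂)p/15.
- 3 against 1: 2 × 0.5/15 = 6.7 points (4.0 at p = 30%, 9.3 at p = 70%).
- 5 against 0, the extreme: 5 × 0.5/15 = 16.7 points.
- Usual standard error for two arms of 15 at 50%: √(2 × 0.25/15) = 18.3 points.

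**Equal exits.** These cancel only when true healing is equal. With 60% against 40% and 3 exits each: 18 × 0.6/15 = 72% against 18 × 0.4/15 = 48%, so 24 points instead of 20.

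**Direction and the no-bias case.** With leaver share d and healing q among leavers, the proportion among those who stay is (p − dq)/(1 − d). At p = 50% and d = 25%: q = 0 gives 0.50/0.75 = 66.7%; q = 20% gives 0.45/0.75 = 60%; q = 50% gives 0.375/0.75 = 50%, no bias; q = 80% gives 0.30/0.75 = 40%. The sign depends on who leaves.

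**With everyone kept.** Take 3 leavers against 1 at p = 50%, so 18 and 16 randomised. Counting leavers by their last, unhealed status gives 9/18 = 50% against 8/16 = 50%, a difference of 0. Bounds, as the 3-leaver arm minus the 1-leaver arm:
- Its leavers healed, the other arm's unhealed: 12/18 − 8/16 = 66.7% − 50.0% = +16.7 points.
- The reverse: 9/18 − 9/16 = 50.0% − 56.3% = −6.3 points.

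No size can be given for healing rate, because the protocol states no mean or standard deviation for it.

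**The case against.** Several objections have force.

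- **Exclusion is not stated.** This is correct. Replacing leavers does not forbid analysing them. A reader might infer that the protocol prescribes an analysis of completers; it does not. The stated purpose points that way, and nothing else in the text decides it.
- **Patients treated off protocol.** A reader might also infer that a patient who receives extra treatment is lost to follow-up or to the comparisons. The documents do not support this. The weekly and 6-month visits apply to all patients with no exception for extra treatment, and efficacy aim 4, "To determine ulcer outcome and need for retreatment in arm 1 versus arm 2", treats retreatment as something to be observed. The gap concerns patients who stop attending.
- **Failing patients leaving.** It is tempting to say that the bar on further treatment forces them out. No text says so. Compression and weekly review continue for all, and arm 2 has an ablation scheduled at 3 months. Outcome-related leaving is possible here, not shown.
- **Size.** Five per arm is a ceiling, not a forecast. The moderate case is about 0.4 of a standard error (6.7/18.3). That is fair, but a confidence interval shows sampling error and does not show bias from exclusion.

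I give no false-positive rate for the chi-square test. It would depend on whether a continuity correction is used, which the protocol does not say.

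**Conclusion.** The point holds for patients who leave. The plan replaces them to protect the analysed number, names no analysis set and has no rule for their outcomes, so following it permits a comparison of completers that may be biased.

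The size is conditional. With 50% true healing and unhealed, excluded leavers, the spurious difference is about 7 points for 3 leavers against 1 and 17 in the extreme case. If leaving is unrelated to healing it is zero; if mainly healed patients leave, the sign reverses. The documents do not settle which arm would lose more patients, so no claim that the plan favours one arm is supported. The change should be made because it is cheap and protects the randomised comparison, not because serious bias has been shown.

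**What to change.** Keep replacement if it is wanted, and add the following:

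1. Analyse every randomised patient in the assigned arm, including those who left and were replaced, in both comparisons.
2. Define early termination. State that off-protocol treatment of the study ulcer is not early termination and does not trigger replacement.
3. For patients who stop attending, use the last weekly ulcer assessment, both for healed status and for healing rate (change in ulcer size over the time observed).
4. Report the number of leavers per arm.
5. Bound the between-arm difference in healed proportion by counting leavers as healed in one arm and unhealed in the other, then the reverse. Counting all leavers as healed in both arms would not bound the difference.

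**Cost.** Some protocol wording, with no extra patients, visits or procedures. The weekly visits are already planned, but Methods lists ulcer size only for the 3- and 6-month visits, so it may have to be recorded weekly (the attached variable sheet, not shown, may already cover this). Healed proportions may look less favourable. Last-visit status is a simple imputation that scores anyone who leaves with an open ulcer as unhealed, which is why the bounds are needed; with few patients they will be wide.
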